**Exploratory Analyses:**

(1) To study the effects of CBD on cognition, anxiety, psychosis, sleep, daytime sleepiness, mood, fatigue, pain, impulsivity, other motor and non-motor PD signs, restless legs syndrome and REM sleep behavior disorder and global impression of patients and clinicians.

(2) To evaluate the effects of CBD on these conditions at a low dose.

**Exploratory Outcome Measures:** The effects of CBD on cognition, anxiety, psychosis, sleep, daytime sleepiness, mood, fatigue, pain, impulsivity, and motor and non-motor PD signs, restless legs syndrome, REM sleep behavior disorder and quality of life are evaluated using the aforementioned assessment tools. The change from baseline to 10th day of 5 mg/kg/day (low dose analysis) and from baseline to the maximum tolerated or targeted dose is compared.

**Table 1.** Measurement tools performed in Stage 1 and Stage 2.

Assessments	Stage 1		Stage 2		
	Primary	Secondary	Primary	Secondary	Exploratory

MoCA	X	X	X		X
Detailed cognitive battery			X		X
Anxiety short form	X	X	X		X
NPI	X	X	X		X
SCOPA-Sleep	X	X	X		X
Depression short form	X	X	X		X
Emotional and Behavioral dyscontrol short form	X	X	X		X
Fatigue Severity Scale	X	X	X		X
Pain Intensity 3a and Interference 4a short forms	X	X	X		X
QUIP-RS	X	X	X		X
MDS UPDRS total	X	X	X	X*	X
Unified Dyskinesia Rating Scale (UDysRS)	X	X	X		X
Rapid Paced Walk (RPW) test			X		X
REM Sleep Behavior Disorder Screening Questionnaire (RBDSQ)	X	X	X		X
The Columbia-Suicide Severity Rating Scale (C-SSRS)	X		X		
International Restless Legs Syndrome Study Group Rating Scale (IRLS)	X	X	X		X
PDQ-39			X		X
EQ-5D			X		X
CGI		X			X
PGI		X			X

\*Specifically items 3.17 and 3.18 in part III

## B. Description of Population to be Enrolled:

Parkinson disease - Persons with PD have progressive disabling tremor, slowness, stiffness, balance impairment, cognitive deficits, psychiatric symptoms, autonomic dysfunction, fatigue and insomnia. Tremor may interfere with necessary daily and work functions. The disorder affects approximately seven million people globally [Yao, S.C, et al. 2013; de Lau LM, et al. 2006]. PD usually begins around age 60, but it can start earlier. Treatment, typically medications such as levodopa and dopamine agonists, improve early stage

symptoms. As the disease progresses and dopaminergic neurons continue to be lost, these drugs become less effective, and levodopa produces disabling motor fluctuations in most patients. PD invariably progresses with time. Untreated individuals are expected to lose independent ambulation after an average of eight years and be bedridden after ten years [Poewe W. 2006]. In people taking levodopa the progression of symptoms to a stage of high dependency from caregivers is on average 15 years.

## **C. Study Design and Research Methods**

### **C.1 Study design and study drug dose determination**

The study is conducted in two stages. The major purpose of the Stage 1 is to study the safety and tolerability of the proposed dosage regimen, which is based on GW Pharmaceutical's experience. This is an open label study in 10 subjects, during which the dose is gradually increased to the manufacturers recommended target dose, with tolerability being evaluated at each dose level. Based on the response of subjects in the Stage 1, a target dose is determined for the next stage. Standardized tools will be administered to study both tolerability and efficacy. Efficacy assessments are simply explorative, and are done to look for an effect that warrants specific or different evaluation in the next stage. We will be recruiting up to 20 subjects in Stage 1 to end up with 10.

The major purpose of Stage 2 is to assess the safety and tolerability of the Epidiolex at the determined dose, and secondarily to study efficacy, particularly regarding tremor. The study has been powered to detect a clinically significant reduction in tremor, all other efficacy analyses are exploratory. Stage 2 is a crossover, double-blind, randomized controlled trial (RCT) with 50 subjects. We will be recruiting up to 60 subjects in Stage 2 to end up with 50.

See Appendix 1 Schedule of Events for each Stage for more detail on study design.

The study drug is obtained from GW Pharmaceuticals and is called Epidiolex. How the dose is started and escalated and what target dose is chosen is based on human literature but primarily on recommendations from GW staff. Animal data supports the use of CBD dosing up to 24 mg/kg/day. In human literature CBD has been well tolerated up to 1500 mg/day (~21 mg/kg/day). Studies using Epidiolex are described in GW's Investigational Brochure (IB) Edition 8, Section 7.3.1. Epidiolex has been used in six Phase 2 studies (mostly related to pain). Presently a study of patients with psychosis are taking 1000 mg per day. Also GW has initiated a clinical program of Phase 1-3 studies to investigate its effect in severe forms of epilepsy, i.e., Davet's syndrome and Lenox Gastaut syndrome. Based on their experience, GW has recommended the dose escalation and target used in this study. As noted, the purpose of Stage 1 study, n=10, is to check for tolerability of this dose regimen in PD patients. If Stage 1 shows that the maximal dose tolerated is less than 20 mg/kg/day, then the maximal targeted dose for the RCT study will be reduced accordingly.

A recent publication, Lancet Neurol 2016; 15: 270-78, shows evidence for using this dose. The study reported on the safety (n=128) and efficacy (n=137) of the study drug we are using, but in a pediatric (aged 1-30; mean

10) population with severe epilepsy. Subjects were evaluated after 12 weeks on study drug, mean dose of ~23 mg/kg/day. Adverse events were reported in 128 (79%) of the 162 patients within the safety group. Adverse events reported in more than 10% of patients were somnolence (25%), decreased appetite (19%), diarrhea (19%), fatigue (13%), and convulsion (11%). Somnolence and fatigue were not dose related, diarrhea and weight loss occurred more often in subjects taking >15 mg/kg/day. Of note, the concomitant use of clobazam (an anticonvulsant medication) was highly associated with somnolence, meaning somnolence was less in those not on clobazam (21%) compared to those taking it (51%). Most adverse events were moderate and transient. SAEs deemed related to the study drug occurred in 12% of subjects, including 9 who had status epilepticus. However, of note, the study showed a ~50% reduction in seizures on study drug, and status epilepticus is a common problem in the population studied. Five subjects (3%) stopped the study drug due to an adverse event. Please see the article regarding clinically significant changes in safety blood analyses. Hepatotoxicity (< 1%), hyperammonemia (<1%), and thrombocytopenia (<1%) occurred only in subjects also taking valproate.

The maximum tolerated doses, in mg/kg/day, of the 10 subjects will be averaged, and adjusted to the next highest 5 mg/kg/day. That dose will be used as the targeted dose for the RCT. For example if the average of the maximal tolerated doses in Stage 1 subjects is 17.4 mg/kg per day, the targeted dose in the RCT will be 20 mg/kg/day. Or if the average of the maximal tolerated doses in stage 1 subjects is 22.7 mg/kg per day, the targeted dose in the RCT will be 25 mg/kg/day.

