## IV. Research Methods

### A. Outcome Measure(s):

#### **Stage 1: Open Label Dose Escalation Tolerability Study**

**Primary Specific Aim:** To confirm that the dosage regimen of CBD, in the form of Epidiolex recommended by the study drug manufacturer is safe and tolerated in 10 subjects with PD. Epidiolex is started at 5 mg/kg/day and is increased every 3 days by 2.5 mg/kg/day to 10 mg/kg/day. Then increase the dosage every 5 days by 5 mg/kg/day to a target dose of 20 mg/kg/day.

**Primary Outcome Measures:** The safety and tolerability of Epidiolex is measured in 4 ways:

1. By examining the frequency of study-related adverse events at each dose level.  
Adverse events are measured primarily by a standardized phone script administered at each dose level. The phone script starts with an open ended question (Do you notice any effects, good or bad, of the study drug?) and followed by a series of yes/no questions regarding adverse effects (including previously reported adverse effects of CBD and general common adverse effects of medications), and all the effects we hypothesize in the study. For each adverse and beneficial reported effect, further questions will be asked, such as when did the effect start and how is it progressing, etc. In addition, since a major dose limiting effect, per GW, is somnolence, the daytime sleepiness part of the SCOPA-sleep is included in the phone script.

The phone script is administered before each dose increase. This phone call is done by a RN, MD or an advanced practice practitioner (APP). Tolerability is judged by the appropriate clinical staff (APP, neurologist) under the supervision of the PI and sub-I (who are MDs), based on their clinical expertise.

2. By monitoring vital signs, orthostatic blood pressures, physical exam, EKG and labs (hematology, complete metabolic profile, and urinalysis) during study visits.
3. By conducting standardized assessment tools on cognition, anxiety, psychosis, sleep, daytime sleepiness, mood, fatigue, pain, impulsivity, suicidality, and motor and non-motor PD signs during study visits. In addition, since many patients with PD also have restless legs syndrome and REM sleep behavior disorder, assessments for these are also done. The assessment tools are:

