### Dose escalation strategy

Study product will be started at 5 mg/kg/day and increased every 3 days by 2.5 mg/kg/day to 10 mg/kg/day. Then increase the dosage every 5 days by 5 mg/kg/day until the subject reaches a maximum targeted dose (20 mg/kg/day) or experiences intolerable adverse effects, in which case the dose will be dropped to the last tolerated dose, for 10-15 days. Tolerability will be assessed on the third day of each dose between 5-10 mg/kg/day and the fifth day of each dose between 10-20 mg/kg/day and the subject is instructed whether or not to change the dose starting the next day. Once a subject has been on a specific dose for at least 3 days (5-10 mg/kg/day) or 5 days (10-20 mg/kg/day), that dose can be changed for less or more than 3 (5-10 mg/kg/day) or 5 days (10-20 mg/kg/day) and can be changed by a smaller increment (2.5-5 mg/kg/day) as needed for tolerability. The maximal tolerated dose is determined by the PI or co-Investigator that is an MD, based on their clinical expertise.

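### The Stage 1 average-and-round-up rule can set the Stage 2 target at a dose most Stage 1 subjects did not tolerate, and no planned summary counts how many tolerated it

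*Combined protocol and SAP*

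**What the plan says.** Section IV.C.1 introduces the link between the stages: "Based on the response of subjects in the Stage 1, a target dose is determined for the next stage". It then gives the rule: "The maximum tolerated doses, in mg/kg/day, of the 10 subjects will be averaged, and adjusted to the next highest 5 mg/kg/day". It adds: "That dose will be used as the targeted dose for the RCT". Two examples follow. In one, the average for Stage 1 "subjects is 17.4 mg/kg per day, the targeted dose in the RCT will be 20 mg/kg/day"; in the other, it "subjects is 22.7 mg/kg per day, the targeted dose in the RCT will be 25 mg/kg/day".

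The Stage 1 dose escalation strategy (section C.2) sets the ladder: "Then increase the dosage every 5 days by 5 mg/kg/day until the subject reaches a maximum targeted dose (20 mg/kg/day". For a subject with intolerable effects it says: "in which case the dose will be dropped to the last tolerated dose". The same paragraph allows smaller changes of 2.5 to 5 mg/kg/day where tolerability requires them, so a maximal tolerated dose of 17.5 is possible.

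The Stage 1 primary aim is to confirm that the regimen "is safe and tolerated in 10 subjects with PD". The Stage 1 part of the Data Analysis Plan (section F) assesses this in four ways: adverse-event frequency by dose level; vital signs, examination, EKG and labs; the standardized tools; and the proportion who drop out because of intolerance.

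Two other statements bear on the target. Earlier in C.1, the RCT maximum is to come down if Stage 1 finds a maximal tolerated dose under 20 mg/kg/day. Section E says the same with 25 mg/kg/day in place of 20. Neither gives a threshold or a number of subjects.

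**The concern.** The rule takes ten individual tolerability results and keeps only their mean, rounded up. Nowhere do the documents require that any number of subjects tolerated the dose that comes out. Because rounding is always upward and the top two standard levels are 15 and 20, an average only slightly above 15 is enough to carry 20 forward.

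At stake is what Stage 1 can conclude. Its stated purpose is to establish that the regimen is tolerated and to supply a target on that basis. As written, the target could be one that most of the ten subjects had stepped down from, and the planned summaries would not state that number.

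**Working it through.** **Inputs.** The rule and its two examples are in C.1. The cap of 20, the 5 mg/kg/day steps from 10, the return to the last tolerated dose and the optional 2.5 steps are in the C.2 dose escalation strategy. Ten subjects are averaged.

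**Formula.** Target = 5 × ceiling(mean of ten maximal tolerated doses ÷ 5).

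**The plan's own examples.** 17.4 ÷ 5 = 3.48, rounded up to 4, gives 20. 22.7 ÷ 5 = 4.54, rounded up to 5, gives 25. Both reproduce. Rounding to the nearest 5 would turn 17.4 into 15, so only rounding up fits both.

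**Cases where the rule returns 20 with few tolerators.**

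| Maximal tolerated doses | Mean | Target | Tolerated 20 |
|---|---|---|---|
| 9 at 15, 1 at 20 | (9×15 + 20)/10 = 15.5 | 20 | 1 of 10 |
| 9 at 15, 1 at 17.5 | (9×15 + 17.5)/10 = 15.25 | 20 | 0 of 10 |
| 10 at 17.5 | 17.5 | 20 | 0 of 10 |

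For 1 of 10 the exact (Clopper-Pearson) 95% CI is 0.3% to 44.5%.

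**Cases where it does not.**

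- 8 at 15, 1 at 10, 1 at 20: mean 15.0, target 15. If next highest is read strictly, 15.0 moves to 20; the text does not settle this.
- 9 at 10, 1 at 20: mean 11, target 15.
- All non-tolerators at 10: 6 at 20 give (6×20 + 4×10)/10 = 16.0 and return 20; 5 at 20 give 15.0 and return 15. At least 6 of 10 must therefore tolerate 20.
- All non-tolerators at 5: at least 7 must tolerate it, since (7×20 + 3×5)/10 = 15.5.

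On the standard ladder (5, 7.5, 10, 15), 220 dose sets have exactly one subject at 20. Only one of them returns 20, namely the other nine all at 15.

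**How often.** The documents give no distribution of maximal tolerated doses in PD, so these are assumptions.

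- *All others stop at 15.* If each subject tolerates 20 with probability p, then P(target = 20) = 1 − (1 − p)^10. That is 65% at p = 0.10, 89% at p = 0.20 and 97% at p = 0.30. At p = 0.20, the chance of returning 20 with 4 or fewer tolerators is 86%.
- *Some stop at 10.* Exact enumeration with probabilities for 10/15/20:

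| P(10), P(15), P(20) | Target = 20 | Target = 20 with ≤4 tolerators |
|---|---|---|
| 0, 0.8, 0.2 | 89% | 86% |
| 0.1, 0.7, 0.2 | 62% | 58% |
| 0.2, 0.5, 0.3 | 59% | 44% |
| 0.3, 0.5, 0.2 | 25% | 22% |

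**Would the planned summaries show it?** A subject who steps from 20 to a lower dose and completes Stage 1 is not a dropout, so the fourth outcome misses them. Adverse-event frequency by dose level describes events, not whether the dose could be held. The other two outcomes are group means or descriptions.

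**Would Stage 2 be held?** The stopping rules in C.7 hold Stage 2 if, for example, the same related event of grade 3 or above occurs in two or more Stage 1 subjects. C.2 provides for dose reduction at grade 2, so repeated grade 2 step-downs from 20 do not meet that criterion.

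**Statements that do not fit together.** In the 15.5 case, the averaging rule keeps 20, while the earlier sentence in C.1 can be read as lowering it, because nine subjects had a maximum under 20. Section E makes the same promise with 25. The example of 22.7 leading to 25 cannot arise when no Stage 1 subject goes above 20.

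**The case against.** The strongest reply is that the target is only a ceiling. Under the Stage 2 dose escalation strategy (C.3), each subject is titrated as tolerated and falls back if necessary, so nobody is held at a dose they cannot take. A DSMB oversees the study, Stage 1 findings can trigger extra surveillance in Stage 2, and C.7 provides a hold. For a ceiling, rounding up lets subjects who tolerate more reach it. All of this stands, and it limits the consequence for individual subjects. It does not make the target one that Stage 1 showed to be tolerated.

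A reader might go further and make three inferences that the documents do not support.

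- *That the rule nearly always returns 20.* The figures of 65% to 97% assume nobody's maximum is below 15, which nothing in the documents establishes. Reductions are allowed at every level, and one plausible spread above gives only 25%.
- *That the number of tolerators plays no part.* It enters the mean directly. When all others are at 15, the mean is 15 + 0.5x for x tolerators.
- *That the plan offers the averaged dose as its evidence of tolerability.* Sections A and F define Stage 1 tolerability through the four outcomes, and the average is not one of them.

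Nor is the mixing of stepped-down subjects into the high-dose comparison an error: sections A and F intend a comparison at each subject's maximum tolerated or targeted dose.

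**Conclusion.** The point holds in a limited form. The rule as written can carry forward the top Stage 1 dose when most subjects did not tolerate it. The clearest case is 1 of 10 on the standard ladder, or 0 of 10 if 2.5 mg/kg/day steps are used. The risk is high when intolerance is concentrated at the last step and falls quickly when subjects drop to 10 or below. The probabilities rest on assumed dose distributions; the worked cases need only the documents' own rule and ladder.

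The gap is one of reporting and consistency. No Stage 1 tolerability summary counts who tolerated the selected target, and three statements about how the target is set do not agree with one another or with the cap of 20. Because Stage 2 titration is individual, this is an inexpensive improvement to what Stage 1 can conclude and not a demonstrated hazard.

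**What to change.** 1. In the Stage 1 part of the Data Analysis Plan (section F), add to the tolerability outcomes the number of subjects, x of 10 with exact 95% CI, whose maximal tolerated dose was at or above the target that the rule returns.
2. State the conclusion on whether the target is tolerated together with that count, and give it to the DSMB before Stage 2 starts.
3. The sponsor should reconcile the average-and-round-up step in C.1 with three things: the earlier C.1 statement that the target is lowered if the tolerated maximum is under 20; the section E statement using 25; and the Stage 1 cap of 20 in C.2, under which the 22.7 example cannot occur.

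No dose or replacement rule is proposed. The cost is some protocol wording and one summary line from maximal tolerated doses that Stage 1 already determines. The downside is a possibly less favourable statement about the target.

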## **C.2 Stage 1: Open Label Dose Escalation Tolerability Study**

The dose escalation tolerability study will be conducted in 10 subjects (we will be recruiting up to 20 subjects to end up with 10) as an open label study lasting 4 weeks followed by a 2-week safety follow up. Subjects are closely monitored as the dose is titrated. Subjects will have a screening visit, a baseline visit within the next 4 weeks, a final assessment visit when they have been on the maximal tolerated or the targeted study drug dose for 10-15 days, and a safety visit 2 weeks later. The subject is to be on the maximal tolerated or targeted dose for 10-15 days, and return for the final assessment visit on that dose on any of days 10-15. The reason for a range of 10-15 days instead of exactly 10 days is to allow for some flexibility in getting subjects in for the study visit. Subjects will be called on the 3rd day of each dose between 5-10 mg/kg/day and the fifth day of each dose between 10-20 mg/kg/day. During phone calls subjects are monitored for adverse events, especially excessive daytime sleepiness, symptoms of hepatotoxicity, as well as changes in medical history and concomitant medications. At the final assessment visit, urinary CBD and metabolites will be tested. Subjects are also called 3 days after stopping the study drug to check for signs of withdrawal.

To increase compliance with taking study drug, subjects will be asked to fill out a diary at home. The diary will be a record of the date and time subjects take study drug, adverse and beneficial events, and whether they talked to study staff on the phone that day, and if so what they were told to do with the dose. To make sure the diary is recorded correctly, subjects will be asked to mail, email or fax a copy or image of the diary they filled out within 3 days of increasing from 5 to 7.5 mg/kg/day. This is so that diary errors can be corrected early.

Urine collection, storage and transfer for cannabis and metabolites test: The purpose of the urine cannabis and metabolites test is to develop a methodology to quantitate CBD metabolites. Subjects will be given two urine cups, 100 mL each, at the baseline visit. On the phone call before the day of the final assessment visit, subjects will be reminded to collect urine in the morning of the study visit. They are asked to fill each up at least 3/4 full if possible, and to bring them to the visit (no refrigeration needed). Upon arrival of the visit the study coordinator will collect and store the urine cups in a -80°C freezer until shipment. For shipment, samples for each individual will be placed onto a sealable plastic bag together with an absorption pad. All the individual bags will be placed into a large sealable plastic bag with contains absorption material. Samples will be placed onto a Styrofoam box and will be shipped on dry ice. Urine samples will be labeled with the name of the study and the date and time of collection. Urine samples will be shipped for analysis to [name] at iC42 Clinical Research & Development.

### Inclusion & Exclusion criteria

#### Inclusion criteria:

- Male or female subjects between 45 and 78 years of age inclusive.
- Willing and able to give informed consent.
- Idiopathic PD, per UK Parkinson's Disease Society (UKPDS) Brain Bank Clinical Diagnostic Criteria
- Rest tremor amplitude score of  $\geq 2$  in any limb on question 3.17 of the MDS-UPDRS (ON state).
- Anti-parkinsonian medication is fixed for at least 1 month prior to the day the subject starts study drug treatment.
- If MoCA $<22$  subject must have a legally authorized representative (LAR) sign the consent, and must have a designated caregiver that agrees to ensure study protocols followed. This includes accompanying patient to study visits and being available for study phone calls.
- Must have a driver to drive them to and from study visits
- Has a significant other (someone who knows the subject well) that is appropriate for doing the NPI assessment, and agrees to do so
- Agrees to not take more than 1 gram per day of acetaminophen, due to a possible interaction with study drug that could increase risk of hepatotoxicity.

\*\*Note: the LAR (required for those with MOCA $<22$ ), caregiver (required for those with MOCA $<22$ ), and significant other (required for all subjects) may be the same person in some cases. In other cases, these may be different people.

#### Exclusion criteria:

- Known or suspected allergy to cannabinoids or excipients used in the study drug formulation.
- Cannabis is detectable at the screening visit by blood testing or at the baseline visit by urine testing. If cannabis is detected at either the screening or baseline visit, then the subject is a screen fail and may return  $>14$  days later for a repeat screening visit. If cannabis is again detected at either the screening or baseline visit, then the subject is excluded and not allowed to rescreen.
- History of drug or alcohol dependence; defined by prior inpatient stay(s) for this or that patient states s/he has a history of this.
- Use of dopamine blockers within 180 days and amphetamine, cocaine, and MAO-A inhibitors within 90 days of baseline.
- Currently taking tolcapone, valproic acid, felbamate, niacin (nicotinic acid) at  $\geq 2000$  mg/day or nicotinamide (nicotinic acid amide or nicotinamide) at  $\geq 3000$  mg/day, isoniazid and ketoconazole due to risk of liver injury and clobazam and ketoconazole because of risk of toxic interactions with the study drug. These medications need to be stopped 90 days before the baseline visit.

- Unstable medical condition.
- Any of the following laboratory test results at screening:
  - Hemoglobin < 10 g/dL
  - WBC <3.0 x 10^9/L
  - Neutrophils <1.5 x 10^9/L
  - Lymphocytes < 0.5 x 10^9/L
  - Platelets <100 x 10^9/L
  - Hemoglobin A1C > 9%
- Aspartate aminotransferase (AST) and/or alanine aminotransferase (ALT) > 3 times the upper limit of normal. Persons with stable liver disease of known etiology can be included, unless total bilirubin or prothrombin time/INR is abnormal.
- Is pregnant or lactating, or has a positive pregnancy test result pre-dose.
- If a sexually active female, is not surgically sterile or at least 2 years post-menopausal, or does not agree to utilize an effective method of contraception from screening through at least 4 weeks after the completion of study treatment, using one of the following: barrier methods (diaphragm or partner using condoms plus use of spermicidal jelly or foam, preferably double-barrier methods); oral or implanted hormonal contraceptive; intrauterine device (IUD); or vasectomized male partner.
- Planned elective surgery during study participation.

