We will follow the FDA's Guidance for evaluating and monitoring potential drug-induced hepatotoxicity. Subjects with stable liver disease can be included if they have a normal total bilirubin and prothrombin time/INR at baseline. Liver function tests (ALT, AST, ALP and bilirubin) will be drawn at baseline and at each visit while subjects are on study drug. In addition, if these labs are abnormal at the end of study visit they will be repeated at the safety follow up visit two weeks later and repeated until back to baseline values. During each phone call that assesses effects of study drug, nonspecific symptoms of Drug Induced Liver Injury (DILI) will be checked, e.g., anorexia, nausea, fatigue, right upper abdominal discomfort, and vomiting. If symptoms indicative of DILI occur the subject will return to clinic immediately for measurement of laboratory signs of hepatic injury, regardless of when the next visit or monitoring interval is scheduled. At any time if aminotransferase enzymes are greater than 3x upper limit of normal (ULN), we will repeat ALT, AST, ALP and bilirubin within 48-72 hours. If symptoms persist or repeat testing shows aminotransferase >3xULN for subjects with normal baseline measures or 2-fold increases above baseline values for subjects with elevated values before drug exposure, we will initiate close observation to determine whether the abnormalities are improving or worsening. Per the FDA, close observation includes:

- Repeating liver enzyme and serum bilirubin tests two or three times weekly. Frequency of retesting can decrease to once a week or less if abnormalities stabilize or the trial drug has been discontinued and the subject is asymptomatic.
- Obtaining a more detailed history of symptoms and prior or concurrent diseases.
- Obtaining a history of concomitant drug use (including nonprescription medications and herbal and dietary supplement preparations), alcohol use, recreational drug use, and special diets.
- Ruling out acute viral hepatitis types A, B, C, D, and E; autoimmune or alcoholic hepatitis; NASH; hypoxic/ischemic hepatopathy; and biliary tract disease.

- Obtaining a history of exposure to environmental chemical agents.
- Obtaining additional tests to evaluate liver function, as appropriate (e.g., INR, direct bilirubin).
- Considering gastroenterology or hepatology consultations.

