We will gather further history as recommended. Unless we find that the repeat testing shows the aminotransferase levels decline to baseline, we will consult the UCH Hepatology team to determine further management.

The FDA advises that since transient fluctuations of ALT or AST are common, and progression to severe liver injury or failure is uncommon, automatic discontinuation of trial drug upon finding a greater than 3xULN elevation of ALT or AST may be unnecessary. The decision of whether to stop study drug will be affected by information on related drugs, the accumulating clinical experience, the clinical status of the patient, and many other factors. We will consult the UCH hepatology service and keep the following FDA guidance in mind. The FDA states that discontinuation of treatment should be considered if:

ALT or AST >8xULN

ALT or AST >5xULN for more than 2 weeks

ALT or AST >3xULN **and** (TBL >2xULN **or** INR >1.5)

ALT or AST >3xULN with the appearance of fatigue, nausea, vomiting, right upper quadrant pain or tenderness, fever, rash, and/or eosinophilia (>5%)

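### The stable-liver-disease allowance sets no ALT/AST ceiling; read as an exemption from the 3×ULN exclusion, it conflicts with the protocol's own liver thresholds

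*Combined protocol and SAP*

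**What the plan says.** **Entry.** One bullet of the Stage 1 exclusion criteria (section IV.C.2) excludes on AST and/or "alanine aminotransferase (ALT) > 3 times the upper limit of normal". It continues: "Persons with stable liver disease of known etiology can be included, unless total bilirubin or prothrombin time/INR is abnormal". Section IV.D repeats the allowance: "Subjects with stable liver disease can be included if they have a normal total bilirubin and prothrombin time/INR at baseline". Neither place gives an ALT or AST limit for these subjects. Section IV.C.3 applies the same criteria to Stage 2, adding only that Stage 1 participants are excluded.

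**Monitoring (section IV.D).**
- Liver tests are drawn at baseline and at each on-drug visit.
- For any aminotransferase above 3×ULN, "we will repeat ALT, AST, ALP and bilirubin within 48-72 hours".
- Close observation starts if symptoms persist, or on a laboratory trigger. With a normal baseline the trigger is a repeat value above 3×ULN. With a raised baseline it is "2-fold increases above baseline values for subjects with elevated values before drug exposure, we will initiate close observation". Close observation includes "Repeating liver enzyme and serum bilirubin tests two or three times weekly".
- Unless the repeat has fallen to baseline, "we will consult the UCH Hepatology team to determine further management".
- Citing FDA guidance, the section says "discontinuation of treatment should be considered if" any of several conditions is met. These include ALT or AST above 8×ULN, above 5×ULN lasting more than 2 weeks, and above 3×ULN with new symptoms such as fatigue or nausea.

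**The concern.** The exclusion and the allowance share a bullet, and the allowance depends only on bilirubin and PT/INR. Two investigators could therefore reach opposite eligibility decisions on the same subject with stable liver disease and ALT above 3×ULN. If the allowance is an exemption, it admits people at enzyme levels that the monitoring section treats as grounds for retesting or for considering withdrawal. For high enough baselines, the trigger for intensive testing then lies above a level at which stopping is to be considered. Section IV.C.9 lists elevated liver function tests among the side effects of CBD, so the question is relevant to subject safety. It does not affect the sample size or the efficacy analysis.

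**Working it through.** The plan states no figure to reproduce here. The check compares its rules with one another.

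**Step 1: which reading?** No other criterion excludes stable liver disease; the nearest excludes an unstable medical condition. A sentence saying such people can be included therefore has most work to do as an exemption from the enzyme limit beside it. The narrower reading makes it an extra condition (normal bilirubin and PT/INR) for people with known liver disease, with 3×ULN still binding. The restatement in section IV.D does not settle the matter.

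**Step 2: thresholds against baseline.** Let *b* be baseline ALT or AST in multiples of ULN, and take the raised-baseline trigger as 2*b*.

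- 2*b* > 5 when *b* > 2.5.
- 2*b* > 8 when *b* > 4.

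| Baseline *b* | Eligible under | Trigger 2*b* | Against 5×ULN | Against 8×ULN |
|---|---|---|---|---|
| 2.5 | either reading | 5.0 | equal | below |
| 2.6 | either reading | 5.2 | 0.2 above | below |
| 3.0 | either reading | 6.0 | 1.0 above | below |
| 3.5 | exemption only | 7.0 | 2.0 above | below |
| 4.0 | exemption only | 8.0 | 3.0 above | equal |
| 4.5 | exemption only | 9.0 | 4.0 above | 1.0 above |
| 6.0 | exemption only | 12.0 | 7.0 above | 4.0 above |

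If the 3×ULN limit binds everyone, 2*b* is at most 6 and the 8×ULN level is never passed.

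**Step 3: an example on the exemption reading.** A subject enters at 6×ULN with normal bilirubin and PT/INR. Every unchanged panel exceeds 3×ULN and calls for a repeat. After 2 weeks the subject meets the consideration for values above 5×ULN with no change in liver status. The laboratory trigger for close observation is 2 × 6 = 12×ULN, above the 8×ULN consideration.

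**Step 4: the smaller gap under either reading.** For *b* from 2.5 to 3.0, testing two or three times weekly is not mandated for an asymptomatic subject on treatment until a repeat value reaches 2*b*, that is 5 to 6×ULN. Using the lower of 2*b* and 5×ULN would make the trigger 5/2.6 = 1.92 times baseline at *b* = 2.6 and 5/3 = 1.67 times baseline at *b* = 3.0.

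**Assumption.** A 2-fold increase above baseline is taken as twice baseline. Read as baseline plus two further multiples (3*b*), the trigger would be 7.5×ULN at *b* = 2.5 and 9.0×ULN at *b* = 3.0. The reading used is the one more favorable to the plan.

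**The case against.** The strongest reply is that liver follow-up is already substantial. Any value above 3×ULN is repeated within 48 to 72 hours, and hepatology is consulted unless levels fall to baseline. Persisting symptoms start close observation at any enzyme level. The high-dose phone calls in Stage 2 (12th and 22nd day) check for symptoms of hepatotoxicity. Abnormal end-of-study values are repeated until back to baseline. The listed levels are considerations, not stopping rules. Sections IV.C.2 and IV.C.7 also stop drug for related grade 3 or 4 events, although the documents do not give the CTCAE liver grades, so the overlap cannot be shown. All of this stands, and it keeps the monitoring gap small.

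A reader might infer that a raised-baseline subject in Stage 2 goes unwatched between the 20 mg/kg/day visit (days 18 to 21) and the end-of-phase visit (day 49 ± 4). That interval is 45 − 21 = 24 to 53 − 18 = 35 days, longer than the 2 weeks in the 5×ULN consideration. The documents do not support that inference. Any value above 5×ULN also exceeds 3×ULN, so it leads to an early repeat and, unless levels fall to baseline, to hepatology review. Such a subject is not followed by scheduled panels alone.

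A reader might also infer that PT/INR cannot be applied as an entry condition because the listed laboratory panels omit it. Staff must obtain it to apply the criterion, so this is only missing detail.

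It can fairly be said that an enzyme ceiling would remove an exemption the authors may have meant. That does not rescue the present wording: on that intent, the entry rule and the liver thresholds still do not fit together.

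**Conclusion.** The point holds for the entry rule and is minor. The allowance has no ALT/AST ceiling, and its favored reading conflicts with the protocol's own thresholds: entry is possible above 3×ULN or 5×ULN, and for baselines above 4×ULN the close-observation trigger passes 8×ULN. A reader might infer that the protocol definitely admits subjects above 3×ULN. The text does not go that far, because the narrower reading remains open and removes the 8×ULN conflict.

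The monitoring gap for baselines of 2.5 to 3.0×ULN is secondary. It does not depend on the allowance and is at most 1.0×ULN above the 5×ULN level. It concerns only asymptomatic subjects on treatment, for whom repeat testing and hepatology review (unless levels fall to baseline) are already required. The documents give no count of eligible people with raised enzymes, so the number affected is unknown and may be zero.

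**What to change.** In section IV.C.2 (and so for Stage 2) and in section IV.D, replace the allowance with one sentence: *a person with stable liver disease of known cause may enter only if ALT and AST are not above 3×ULN and total bilirubin and PT/INR are normal.* Stable liver disease remains admissible. The cost is a wording change and possibly a very small loss of eligible subjects.

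Optionally, in section IV.D, start close observation for raised-baseline subjects at the lower of twice baseline and 5×ULN. With the entry ceiling in place this cap never acts below 1.67 times baseline. It costs a few extra liver tests, some prompted by the transient fluctuations that section IV.D calls common. That section already lets testing drop to weekly or less once values stabilize. Whether the cap matches the FDA guidance the protocol follows cannot be checked from the documents; 5×ULN is proposed only because section IV.D itself names that level.
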